16.0 Statistical Considerations and Methodology

16.1 Overview:

This is a phase II study of Nivolumab in patients with relapsed or refractory peripheral T-cell lymphoma (PTCL). It will use a one-stage design with an interim analysis based on a Simon optimal design to assess efficacy.

- 16.1.1 Endpoint: The primary endpoint in this trial is the proportion of objective responses (either a CR or PR according to the revised Lugano Classification Response criteria (Cheson et al, 2014)). For the primary endpoint, CR or PR will be considered synonymous with “success”, unless specified otherwise. All patients meeting the eligibility criteria who have signed a consent form and have begun treatment will be evaluable for response.

16.2 Statistical Design

16.2.1 Decision Rule

In a previous phase II single arm trial of 130 confirmed PTCL patients receiving Romidepsin (14 mg/m² as a 4 hour transfusion on Days 1, 8 and 15 of 28 day cycles), 25% achieved a response (CR/CRu + PR). The CR/CRu rate was 15%. A second phase II single arm study of 111 treated PTCL patients receiving Pralatrexate (30 mg/m²/wk intravenously for 6 weeks in 7-week cycles) showed a 29% response rate (CR + PR) with 11% having CR. This study will include patients with histologically proven TCL who will be receiving nivolumab (240mg every 2 weeks for 4 months, then 480mg every 4 weeks). It is expected that this dose will have a complete response rate similar to those presented above. The largest success proportion where the proposed treatment regimen would be considered ineffective in this population is 10%, and the smallest success proportion that would warrant subsequent studies with the proposed regimen in this patient population is 30%. This design uses 35 evaluable patients to test the null hypothesis that the true complete response rate is at most 10%.

- 16.2.1.1 Interim Analysis: Enter 12 evaluable patients into the study. If there are one or no successes observed in the first 12 evaluable patients, we will consider this regimen ineffective in this patient population and terminate this study. Otherwise, if the number of successes is at least 2, we will continue accrual.
- 16.2.1.2 Final Decision Rule: If 5 or fewer successes are observed in the first 35 evaluable patients, we will consider this regimen ineffective in this

patient population. If 6 or more successes are observed in the first 35 evaluable patients, we may recommend further testing of this regimen in subsequent studies in this population.

- 16.213 Over Accrual: If more than the target number of patients are accrued, the additional patients will not be used to evaluate the stopping rule or used in any decision making process. Analyses involving over accrued patients are discussed in Section 16.34.
- 16.214 NOTE: We will not suspend accrual at the interim analysis to allow the first 12 patients to become evaluable, unless undue toxicity is observed. Given the limited overall sample size and the inclusion of an adverse events stopping rule, we feel it is ethical to not halt accrual for the interim analysis. However, if accrual is extremely rapid, we may temporarily suspend accrual in order to obtain safety data on these patients before re-opening accrual to further patients.
- 16.22 Sample Size: This study is expected to require a minimum of 12 and a maximum of 35 evaluable patients. We anticipate accruing 4 additional patients to account for ineligibility, cancellation, major treatment violation, or other reasons. Therefore, the study is expected to accrue a maximum of 39 patients overall.
- 16.23 Accrual Rate and Study Duration: The anticipated accrual rate is 10 evaluable patients per year. Therefore, the accrual period is expected to be 3 years. The primary endpoint will be evaluated approximately 3.5 years after the trial opens, or after the last patient accrued has been observed for at least 6 months and data collection for the induction phase is complete. The total study duration is expected to be approximately 5.5 years, or until all patients have completed all cycles of treatment.
- 16.24 Power and Significance Level: Assuming that the number of successes is binomially distributed, the significance level is .10, i.e. there is a 10% chance of finding the drug to be effective when it truly is not. The probability of declaring that this regimen warrants further study (i.e. statistical power) under various success proportions and the probability of stopping accrual after the interim analysis can be tabulated as a function of the true success proportion as shown in the following table.

If the true success proportion is...	0.10	0.15	0.20	0.25	0.30
Then the probability of declaring that the regimen warrants further study is...	0.098	0.337	0.604	0.795	0.901
and the probability of stopping after the interim analysis is ...	0.659	0.444	0.275	0.158	0.085

- 16.25 Other considerations: Adverse events, quality/duration of response, and patterns of treatment failure observed in this study, as well as scientific discoveries or changes in standard care will be taken into account in any decision to terminate the study
- 16.3 Analysis Plan
 - 16.31 Primary Outcome Analyses:

- 16.311 Definition: The primary endpoint of this trial is the proportion of complete or partial responses to therapy. A success is defined as a CR or PR as the objective status during therapy. All patients meeting the eligibility criteria who have signed a consent form and have begun treatment will be evaluable for response.
- 16.312 Estimation: The proportion of successes will be estimated by the number of successes divided by the total number of evaluable patients. Confidence intervals for the true success proportion will be calculated.
- 16.32 Secondary Outcome Analyses: These analyses will include all patients meeting the eligibility criteria who have signed a consent form and have begun treatment, including patients who fail to achieve a complete response.
- 16.321 Response: Response rates will be estimated using complete and partial metabolic responses (CMR or PMR) divided by the total number of evaluable patients. All evaluable patients will be used for this analysis. These rates will be compared to the primary endpoint to explore any differences in the measurement method.
- 16.322 Adverse Events: All eligible patients that have initiated treatment will be considered evaluable for assessing adverse event rate(s). The maximum grade for each type of adverse event will be recorded for each patient, and frequency tables will be reviewed to determine patterns. Additionally, the relationship of the adverse event(s) to the study treatment will be taken into consideration.
- 16.323 Progression free survival time is defined for all evaluable patients who have achieved a CR/CMR or PR/PMR as the time from registration to relapse or death due to any cause. The distribution of progression-free survival will be estimated using the method of Kaplan-Meier. In addition, the progression-free survival rate at 5 years after registration will be reported.
- 16.324 Duration of response is defined for all evaluable patients who have achieved a CR/CMR or PR/PMR as the date at which the patient's objective status is first noted to be a CR/CMR or PR/PMR to the earliest date relapse is documented. The distribution of duration of complete response will be estimated using the method of Kaplan-Meier
- 16.325 Overall survival time is defined as the time from registration to death due to any cause. The distribution of survival time will be estimated using the method of Kaplan-Meier(Kaplan and Meier 1958). In addition, the overall survival rate at 2 years after registration will be reported.
- 16.33 Correlative Analyses
- 16.331 Correlative analyses will be exploratory in nature and will include evaluation of T-cell activation, cytokine up regulation, biomarker activity with respect to response to therapy (intratumoral cell populations, genetic variability, serum cytokines, T-cell activation), and PD-L1/PD-1/PD-L2 expression. These factors will be summarized and used to help characterize the types of patients accrued to this trial. In addition, we will explore differences in the distributions of these

risk factors by clinical outcome (progression-free survival status at 5 years and whether the patient remains in sustained CR/CMR/PR/PMR). Nonparametric quantitative comparisons by group will be made as appropriate (Fisher's exact or Wilcoxon rank sum). Kaplan-Meier methods and log-rank statistics will be used to compare between groups for time-to-event measures. Given the limited number of patients, the difference in risk factor distribution by outcome will be largely exploratory.

- 16.34 Over Accrual: If more than the target number of patients are accrued, the additional patients will not be used to evaluate the stopping rule or used in any decision making processes; however, they will be included in final endpoint estimates and confidence intervals.

16.4 Data & Safety Monitoring:

- 16.41 The principal investigator(s) and the study statistician will review the study at least twice a year to identify accrual, adverse event, and any endpoint problems that might be developing. The Mayo Clinic Cancer Center (MCCC) Data Safety Monitoring Board (DSMB) is responsible for reviewing accrual and safety data for this trial at least twice a year, based on reports provided by the MCCC Statistical Office.

- 16.42 Adverse Event Stopping Rules: The stopping rules specified below are based on the knowledge available at study development. We note that the Adverse Event Stopping Rule may be adjusted in the event of either (1) the study re-opening to accrual or (2) at any time during the conduct of the trial and in consideration of newly acquired information regarding the adverse event profile of the treatment(s) under investigation. The study team may choose to suspend accrual because of unexpected adverse event profiles that have not crossed the specified rule below.

Accrual will be temporarily suspended to this study if at any time we observe events considered at least possibly related to study treatment (i.e. an adverse event with attribute specified as "possible," "probable," or "definite") that satisfy one of the following:

- if 4 or more patients in the first 10 treated patients (40%) experience a grade 4 or higher non-hematologic adverse event at least possibly related to treatment.
- if after the first 10 patients have been treated, 40% of all patients experience a grade 4 or higher non-hematologic adverse event at least possibly related to treatment.

We note that we will review grade 4 and 5 adverse events deemed "unrelated" or "unlikely to be related", to verify their attribution and to monitor the emergence of a previously unrecognized treatment-related adverse event.

16.5 Results Reporting on ClinicalTrials.gov:

At study activation, this study will have been registered within the "ClinicalTrials.gov" website. The Primary and Secondary Endpoints along with other required information for this study will be reported on ClinicalTrials.gov. For purposes of timing of the Results Reporting, the initial estimated completion date for the Primary Endpoint of this study is

5.5 years after the study opens to accrual. The definition of “Primary Endpoint Completion Date” (PECD) for this study is at the time the last patient registered has been followed for at least 2 months.

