2.0 Goals

2.1 Primary

To assess the clinical benefit of nivolumab in T-cell lymphomas, as measured by objective response rate (ORR) within 12 cycles according to the Lugano Classification Response Criteria (2014) ([Section 11.0](#))

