7.0 Protocol Treatment

7.1 Treatment Schedule

7.11 Treatment Schedule

Agent	Dose Level	Route	Day	Cycle Length
Nivolumab	240mg	IV	Cycles 1-8 Day 1	Every 14 days for 8 cycles
	480 mg	IV	Beginning Cycle 9, Day 1	Every 28 days for a maximum of 24 cycles (Total of 32 cycles)

No routine premedications are needed with nivolumab administration.

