13.5 Maximum cycles for patients who achieve CR/CMR

Patients who achieve a CR/CMR will receive a maximum total of 32 cycles (i.e 2 years of therapy). After 2 years, they should be observed (see Section 13.4 above).

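### Section 16.23 understates accrual by half a year and lets the primary analysis run before the last cycle-12 scan; the completion definition in 16.5 fits neither its own 5.5-year date nor 16.23

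*Combined protocol and SAP*

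**What the plan says.** **Numbers and rate.** Section 16.22: "This study is expected to require a minimum of 12 and a maximum of 35 evaluable patients". With four extra patients for ineligibility and similar losses, "the study is expected to accrue a maximum of 39 patients overall". Section 16.23: "The anticipated accrual rate is 10 evaluable patients per year. Therefore, the accrual period is expected to be 3 years".

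**When the primary endpoint is evaluated.** Section 16.23 puts this at roughly 3.5 years after opening, or "after the last patient accrued has been observed for at least 6 months and data collection for the induction phase is complete". The same paragraph adds: "The total study duration is expected to be approximately 5.5 years, or until all patients have completed all cycles of treatment".

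**What the endpoint is.** Section 2.1 defines it as "objective response rate (ORR) within 12 cycles". Section 16.311 instead counts a CR or PR at any time during therapy, with no cycle limit. The study calendar (4.1) places PET-CT restaging at the end of cycles 4, 8 and 12. Section 7.11 gives 14-day cycles for cycles 1 to 8, then from cycle 9: "Every 28 days for a maximum of 24 cycles (Total of 32 cycles".

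**Registry date.** Section 16.5 estimates primary completion at 5.5 years after opening to accrual. It defines that date as the point when the last registered patient has at least 2 months of follow-up.

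**The concern.** Three timing statements that should describe one event do not agree.

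1. The accrual period is presented as following from the rate, but it does not follow from the rate and the target in the preceding paragraph.
2. The analysis trigger has two conditions: a 6-month floor and completeness of data for an induction phase. The protocol never defines that phase; it speaks of initial treatment (cycles 1 to 8) and continuation. If induction means cycles 1 to 8, neither condition secures the cycle-12 scan, so the plan allows the primary count before the endpoint window in 2.1 has closed for the last patient or patients.
3. The completion definition in 16.5 is much earlier than the 5.5 years printed beside it, and that 5.5 years is also the total study duration in 16.23.

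At stake are a realistic accrual forecast, a complete primary endpoint for a decision that turns on 5 versus 6 successes, and a registry date with one meaning. A response first seen on the cycle-12 scan would be lost by an early cut, and an early cut cannot create one.

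**Working it through.** **Inputs.** 35 evaluable patients and 39 in total (16.22). 10 evaluable per year, 3-year accrual, 3.5-year evaluation, 6-month trigger (16.23). Cycles of 14 days (1 to 8) and 28 days (from 9) (4.1, 7.11). Interim stop at 1 or fewer of 12; success at 6 or more of 35 (16.2). 2-month definition and 5.5 years (16.5).

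**Step 1: accrual period.** Time = patients / rate.
- 35 / 10 = 3.5 years. The stated 3 years gives 10 × 3 = 30 patients, 5 short.
- Using all 39 widens the gap: 39 / 10 = 3.9 years.
- The stated evaluation time is 3 + 0.5 = 3.5 years. With corrected accrual the same trigger falls at 3.5 + 0.5 = 4.0 years.

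**Step 2: trigger against endpoint.**
- End of cycle 12 = 8 × 14 + 4 × 28 = 224 days (32 weeks, 0.61 year).
- Six months = 365.25 / 2 = 182.6 days, during cycle 11.
- Shortfall = 224 − 182.6 = 41.4 days, or 34.4 days at the early edge of the ±7-day scan window.
- End of cycles 1 to 8 = 8 × 14 = 112 days, so an induction phase read that way is complete well before day 183.
- Last patient's cycle-12 restaging: 3.5 + 0.61 = 4.11 years.

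**Step 3: how many patients.** Mean spacing is 365.25 / 10 = 36.5 days.
- Even spacing: at the trigger the last three patients are at days 183, 219 and 256. The last is 41 days short. The one before is 5 days short, inside the ±7-day window. So about one patient is affected.
- Random (Poisson) arrivals: the last patient plus those expected in the preceding 41.4 days, 1 + 41.4 / 36.5 = 2.1 patients on average.
- Early progression or stopping reduces either count.

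**Step 4: effect on the decision.** Exact two-stage binomial: the sum over x = 2 to 12 of P(X₁ = x) × P(X₂ ≥ 6 − x), with X₁ from 12 patients and X₂ from 23. It first reproduces the plan's probabilities of declaring success at 0.10, 0.15, 0.20, 0.25 and 0.30: 0.098, 0.337, 0.604, 0.795 and 0.901. I then removed one or two second-stage patients, meaning their responses are always missed:

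| True response rate | None missed | One missed | Two missed |
|---|---|---|---|
| 0.30 | 0.901 | 0.898 | 0.893 |
| 0.20 | 0.604 | 0.588 | 0.570 |
| 0.10 | 0.098 | 0.090 | 0.082 |

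For a given number of affected patients this is the extreme case, because their cycle-4 (day 56) and cycle-8 (day 112) scans would already be available.

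**Step 5: completion date in 16.5.** Date = accrual + 2/12 year.
- Stated accrual: 3 + 0.17 = 3.17 years, which is 5.5 − 3.17 = 2.33 years before the printed estimate.
- Corrected accrual: 3.5 + 0.17 = 3.67 years, which is 5.5 − 3.67 = 1.83 years before it.
- Two months is 365.25 / 6 = 61 days, against day 183 for the trigger in 16.23 and day 224 for the 12-cycle endpoint.

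**The case against.** **Three years could be an expected duration allowing for the interim stop.** Expected sample size, 12 + 23 × (1 − probability of stopping), is 28.7 at a 20% response rate, 31.4 at 25% and 33.0 at 30%, or 2.9, 3.1 and 3.3 years. But 16.23 does not say it averages over early stopping, and such an average does not describe a trial that reaches its 35-patient maximum. The slip stands.

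**The 6-month condition is a floor.** A reader might infer that the plan requires a cut at day 183. It does not: the wording sets a minimum and adds a data-completeness condition. The problem arises only if the floor is used as the date and induction means cycles 1 to 8. It also depends on 2.1 governing. Under 16.311, day 224 would not close the endpoint at all, and a 6-month cut would fit even less well. What stands is that the rule permits an early cut.

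**Over-accrual can protect the decision.** Section 16.213 restricts the decision to the first 35 evaluable patients, while the trigger follows the last patient accrued. With two further evaluable patients at even spacing, patient 35 is at day 183 + 73 = 256 at the trigger and is complete. This is correct, but it relies on over-accrual happening.

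**Section 16.5 does not give two dates.** A reader might infer two competing completion dates. In fact it gives one estimate and a definition with a floor, which 5.5 years does not breach. It also governs results reporting, not the analysis, so it implies no early data cut. What stands is the mismatch: a definition met 1.8 to 2.3 years before the estimate, and tied to neither 16.23 nor the 12-cycle window.

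**Conclusion.** Minor. The accrual figure is wrong as written: 3.5 years, not 3, with the evaluation date following to about 4.0 years under the existing trigger. Section 16.23 also permits, without requiring, a primary analysis about 41 days before the last cycle-12 restaging. The completion definition in 16.5 agrees with neither its own date nor 16.23.

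A reader might infer that the design is underpowered or that the trial's conclusion is at risk. The documents do not support that. The sample size, alpha and power table rest on 35 patients and are unaffected. Even with two responses always missed, power at 30% is 0.893, and the error moves in the conservative direction.

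The patient counts assume a constant 10 per year and either even or Poisson arrivals. They are not upper limits, since more than two patients could be affected if late accrual bunches. The endpoint argument assumes that 2.1 governs over 16.311 and that induction means cycles 1 to 8.

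**What to change.** **Section 16.23.** State that 35 evaluable patients at 10 per year are expected to take 3.5 years. Remove the reference to an induction phase. Evaluate the primary endpoint when the last of the first 35 evaluable patients has had the end-of-cycle-12 restaging, or has progressed, died or stopped before it (about 4.1 years after opening). Estimates that include over-accrued patients (16.34) use the same condition applied to those patients; the decision does not wait for them (16.213).

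**Section 16.5.** Use the same event and date in place of the 2-month definition and the 5.5-year estimate.

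**Sections 2.1 and 16.311.** The sponsor should reconcile the 12-cycle window with the open-ended during-therapy definition, because the trigger above assumes that 2.1 governs.

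**Cost.** Wording only: no extra patients, visits or scans. The readout moves about 41 days later than the earliest date the current trigger allows, or about 55 days with the 7-day start window (6.6) and the +7-day scan window. Treatment interruptions could add more if restaging follows delayed cycles, although 8.3 says tumor assessments continue on schedule during interruptions. If all 39 patients are evaluable, the estimates that include them are ready at about 3.9 + 0.61 = 4.5 years, against 3.9 + 0.5 = 4.4 under the current trigger.

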2.2 Secondary

2.21 To assess safety and tolerability of the regimen in this patient population

2.22 To assess progression-free survival (PFS)

2.23 To assess duration of response (DOR)

2.24 To assess overall survival (OS)

2.3 Correlative Research

2.31 To evaluate T-cell/cytokine profile in the peripheral blood – peripheral blood specimens will be used to assess T-cell activation and cytokine up regulation as measures of treatment effect. This goal will be exploratory in nature and reported descriptively

- 2.32 To evaluate intratumoral Biomarkers- intratumoral cell populations and distribution, genetic variability, mutational burden and T-cell activation will be evaluated to identify potential biomarkers that correlate with response to therapy. This goal will also be exploratory in nature
- 2.33 To assess the potential association between PD-L1/PD-1/PD-L2 expression on tumor and T cells and/or PD-L1 soluble levels in plasma with clinical efficacy of PD-1 blockade.

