13.7 Definition of Ineligible

A patient is deemed *ineligible* if after registration, it is determined that at the time of registration, the patient did not satisfy each and every eligibility criteria for study entry. The patient may continue treatment off-protocol at the discretion of the physician as long as there are no safety concerns, and the patient was properly registered. The patient will go directly to the event-monitoring phase of the study (or off study, if applicable).

- If the patient received treatment, all data up until the point of confirmation of ineligibility must be submitted. Event monitoring will be required per Section 18.0 of the protocol.
- If the patient never received treatment, on-study material and the End of Active Treatment/Cancel Notification Form must be submitted. No further data submission is necessary.

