13.8 Definition of Major Violation

A patient is deemed a *major violation*, if protocol requirements regarding treatment in Cycle 1 of the initial therapy are severely violated that evaluability for primary end point is questionable. All data up until the point of confirmation of a major violation must be submitted. The patient will go directly to the event-monitoring phase of the study. The patient may continue treatment off-protocol at the discretion of the physician as long as there are no safety concerns, and the patient was properly registered. Event monitoring will be required per Section 18.0 of the protocol.

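### Adverse event rates are limited to eligible treated patients, so anyone dosed and later found ineligible drops out of the safety tables

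*Combined protocol and SAP*

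**What the plan says.** Section 16.322 sets the population for adverse event rates: "All eligible patients that have initiated treatment will be considered evaluable for assessing adverse event rate(s"). Its parent, 16.32, sets the same limit for every secondary analysis: "These analyses will include all patients meeting the eligibility criteria who have signed a consent form and have begun treatment". These tables are the planned analysis of goal 2.21, "To assess safety and tolerability of the regimen in this patient population", and 16.5 commits to posting the secondary endpoints publicly.

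Under 13.7 a patient is ineligible if it emerges after registration that "the patient did not satisfy each and every eligibility criteria for study entry". Failing one criterion is enough. The section provides for patients who have already been treated: "all data up until the point of confirmation of ineligibility must be submitted". It also states: "The patient may continue treatment off-protocol at the discretion of the physician", subject to conditions.

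The stopping rule in 16.42 has a different base. Its first limb applies "if 4 or more patients in the first 10 treated patients (40%) experience a grade 4 or higher non-hematologic adverse event". Only events with a possible or stronger link to nivolumab count, and neither limb mentions eligibility.

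**The concern.** A safety rate should normally describe everyone exposed to the drug. Cancelled patients (13.9) are never dosed, so the requirement that treatment has begun already removes them from 16.322. The eligibility condition can therefore only remove patients who received nivolumab.

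The omitted patients need not resemble the rest. Some eligibility criteria concern risks that the protocol itself names:

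- Prior allogeneic transplant is excluded in 3.26, and 15.199c warns of more graft-versus-host disease and death in such patients.
- A history of pancreatitis is excluded in 3.29d, and pancreatitis is a listed toxicity in 15.17.
- Criterion 3.23 refers directly to the assessment of safety.

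Other failures, such as an unconfirmed histology, may carry equal or lower risk, so the direction of any bias is unknown. As written, an event could also count towards suspending accrual under 16.42 and then be absent from the reported rates.

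**Working it through.** **Plan's own figures.** The plan gives no figure for the adverse event population. The relevant numbers are in 16.22: 35 evaluable patients plus 4 extra, 39 in all. The operating characteristics in 16.24 do not depend on this point. An exact two-stage binomial calculation (stop at 1 or fewer of 12; at least 6 of 35 to succeed) gives 0.0977 at a true rate of 10% and 0.9014 at 30%, matching the tabulated 0.098 and 0.901.

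**Can dosing precede a finding of ineligibility?** Yes. One route is central pathology review, needed only where a Mayo pathologist has not confirmed the diagnosis. It is due within 42 days of registration (17.21). Treatment starts within 7 days of registration (6.6) and is given every 14 days at first (7.11). Starting on day 0 gives doses on days 0, 14 and 28; starting on day 7 gives days 7, 21 and 35. Either way, three doses can come before day 42.

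**Assumptions.** Let k be the number of treated but ineligible patients. The documents do not give k. I take 0 to 4, the upper end being the whole allowance in 16.22, which also covers cancellations, violations and other reasons. I take 35 eligible treated patients. As illustrative event rates q, I use two figures from 1.26, which come from a mixed hematologic population: 4.8% (drug-related pneumonitis as a serious event) and 14.3% (drug-related events leading to discontinuation).

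**Share omitted and chance of losing an event.** The share omitted is k/(35+k). The chance that the omitted patients include at least one event is 1 − (1−q)^k.

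| k | Share omitted | At least one event, q = 4.8% | At least one event, q = 14.3% |
|---|---|---|---|
| 0 | 0/35 = 0% | 0% | 0% |
| 1 | 1/36 = 2.8% | 4.8% | 14.3% |
| 2 | 2/37 = 5.4% | 9.4% | 26.6% |
| 3 | 3/38 = 7.9% | 13.7% | 37.1% |
| 4 | 4/39 = 10.3% | 17.9% | 46.1% |

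**Expected bias when the table shows 5/35 = 14.3%.** If omitted patients have risk ratio RR, the expected all-treated rate is (5 + k × RR × 5/35)/(35 + k).

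- RR = 1: 14.3% for every k, so no bias.
- RR = 0.5 (assumed): 14.1% for k = 1 and 13.6% for k = 4. The table is too high by 0.2 to 0.7 points.
- RR = 2 (assumed): 14.7% for k = 1 and 15.8% for k = 4. The table is too low by 0.4 to 1.5 points.

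For scale, the exact 95% interval for 5/35 is 4.8% to 30.3%.

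**Rare event.** If the only event falls in the one omitted patient, the table shows 0/35 (exact 95% interval 0 to 10.0%) where the all-treated result is 1/36 = 2.8% (0.1% to 14.5%). This is unlikely. Its probability, q(1−q)^35, is greatest at q = 1/36, where it is 1.0%. For four omitted patients, the chance of no event in the 35 and at least one in the four is (1−q)^35 × [1 − (1−q)^4], which is at most 4.0%.

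**The case against.** The strongest reply concerns weight. The tables are descriptive and feed no test or decision rule. The number affected may be zero, and 6.4 has eligibility verified before a registration is accepted. Even the least favourable case shown, four omitted at double risk, moves the rate by 1.5 points, well inside its sampling error. Expedited reporting, DSMB review (16.41) and the stopping rule are not limited to eligible patients. All of this stands, and it is why the point is modest.

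A second reply is that goal 2.21 concerns a defined patient population, and someone whose lymphoma is not confirmed arguably lies outside it. That would justify an eligible-only supplementary table. It does not justify leaving exposed patients out of the only planned rates, and pathology is only one route to ineligibility.

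A third is that a real-time rule has to count patients as they are treated, so the two denominators do not strictly conflict. That is fair; the difference shows only that the plan already uses an all-treated count for safety elsewhere.

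The last is practical. Because 13.7 ends data submission when ineligibility is confirmed and moves the patient to event monitoring, adding these patients could bring in shortened follow-up and dilute the rates. This is a real risk, and the fix needs the clarification in 13.7 to deal with it.

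**Conclusion.** The concern holds. Sections 16.32 and 16.322 expressly confine adverse event rates to eligible treated patients, 13.7 foresees dosed patients outside that set, and nothing elsewhere restores them. The rule in 16.34 on over-accrual adds patients to the final estimates but does not waive eligibility.

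The size is small and partly unknown: 0% to 10.3% of exposed patients omitted, and an expected error between +0.7 and −1.5 points on a 14.3% rate. These figures assume 0 to 4 such patients, 35 eligible treated patients, and a risk between half and double that of the others. The primary result, error rates and stopping rule are unaffected. The change should still be made, because it removes an avoidable gap in the reported safety results at almost no cost.

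**What to change.** Add to 16.322, as a stated exception to 16.32, that adverse event analyses include every patient who received at least one dose of nivolumab, whether or not later found eligible. An eligible-only table can be kept as a supplement.

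In 13.7, state that the data cut-off at confirmation of ineligibility does not override the 100-day adverse event collection in 10.82 and 10.84. Since 13.7 allows treatment to go on off-protocol, also state which dose starts the 100 days. Section 13.8 has a similar cut-off ("All data up until the point of confirmation of a major violation must be submitted") and could carry the same clause. That is a matter of tidiness, since eligible treated violators are already in the 16.322 population.

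The cost is one sentence and one or two clauses. No patients are added, and the primary analysis, decision rule and stopping rule stay as they are. Adverse event denominators rise by an assumed 0 to 4, and rates may move slightly in either direction.
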